4.1 Number/Source/Screening

The trial will accrue a maximum of 1000 patients over a 3-4 year interval. Approximately 500 patient will be randomized to initial trophic feeding and 500 to initial full calorie feeding. The first 272 patients were enrolled in a 2 x 2 factorial design with an Omega 3 Fatty acid rich medical food versus a control isocaloric medical food. This portion of the trial was stopped by the DSMB for futility.

Patients with ALI or ARDS will be recruited from intensive care units at NIH ARDS Network centers. Study coordinators will visit intensive care units daily to identify potential candidates for enrollment (see inclusion criteria, section 4.2, and exclusion criteria, section 4.3. Permission to approach patients and/or their families will be requested from the attending physicians. All patients meeting the inclusion criteria will be entered on a screening log. If the patient is not enrolled, the screening log will include information explaining why enrollment did not occur (exclusion criteria, attending physician denial, patient refusal, etc. see Appendix L).

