Mortality will be compared at interim data analyses using Kaplan Meier estimates at 60 days and their associated standard errors. This analysis will be stratified as above and a test for interaction of treatment with strata will be presented. At the end of the study sixty-day mortality will be compared using a Mantel-Haenzel test as long as all patients can be followed. If not the method used for the interim analyses will be used.

Other Endpoints

The number of ICU-free days, Organ-Failure Free days, and days from first weaning readiness will be analyzed in the same manner as is described above for the primary endpoint. In addition we will test for interactions between treatment and gender and race as per NIH guidelines (National Institutes of Health, 2001).

Changes in plasma levels of IL-6, IL-8, and protein will be compared in two analyses. An analysis of covariance will test for a treatment effect on the day 3 value of these variables using the day 0 value as a covariate. In addition, a multivariate analysis of variance will test for a baseline difference between day 3 and day 0.

Table 3 illustrates the detectable differences for endpoints, assuming 1000 patients enrolled, 90% power, and a two-sided alpha-level of 0.05.

Table 3: Detectable Differences for Secondary Endpoints

Variable	Incidence or Mean	Standard Deviation	Detectable Difference
PaO ₂ / FiO ₂	155	73	15
ICU free days	13.4 days	12.6 days	2.6 days
Shock free days	19.1 days	4.93 days	2.23 days
Plasma IL-6 (pg/ml)	1252	862	177
Plasma IL-8 (pg/ml)	149	93	19
28 day hospital mortality	22%		8.2%
90 day hospital mortality	25.4%		8.6%

Changes in physiologic lung indices on days 1-7 will be compared using a multivariate analysis of variance.

Twice during the early part of the study, the DSMB will evaluate the glucose control between the trophic and full-calorie arms to ensure that the levels of blood glucose are not clinically different between the groups over the first 6 days of the study. These evaluations will occur after approximately 100 and 250 patients are enrolled in the study. Should the blood glucose values differ between the groups at these evaluations, the guidelines for controlling blood glucose levels for the remainder of the study may be adjusted in an attempt to equalize the blood glucose levels for the study.

8 Data Collection and Site Monitoring

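### Table 3, shock-free days: the SD of 4.93 and the detectable difference of 2.23 days cannot both be right, since 4.93 gives 1.01 days and 2.23 needs an SD of about 10.9

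*Protocol*

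**What the plan says.** Under Other Endpoints in Section 7, the protocol introduces Table 3 with a single set of conditions: "Table 3 illustrates the detectable differences for endpoints, assuming 1000 patients enrolled, 90% power, and a two-sided alpha-level of 0.05". No row carries its own sample size, power or method. The shock-free-days row lists a mean of 19.1 days, an SD of 4.93 days and a detectable difference of 2.23 days.

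Section 4.1 gives the allocation: "Approximately 500 patient will be randomized to initial trophic feeding and 500 to initial full calorie feeding". Section 7 says that ICU-free days, organ-failure-free days and days from first weaning readiness "will be analyzed in the same manner as is described above for the primary endpoint", which is an analysis of variance on means. Section 3.2 (item 4) lists organ-failure-free days over five systems, circulation among them. Shock-free days is not a separately listed endpoint, and I read it as the circulatory component.

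**The concern.** Under fixed sample size, power and significance level, the detectable difference between two means is a constant multiple of the SD. Every continuous row of Table 3 should therefore show the same ratio of difference to SD. Four rows show about 0.205. The shock-free-days row shows 2.23/4.93 = 0.45.

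As printed, a reader cannot tell whether the trial was expected to detect about 1 day or about 2.2 days on this measure. That matters for anyone who uses the table to judge how sensitive the planned organ-failure comparison is. It does not touch the primary endpoint.

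**Working it through.** **Inputs**
- Total 1000 patients, 90% power, two-sided 0.05 (Section 7, sentence introducing Table 3).
- About 500 per arm (Section 4.1).
- SDs and stated differences from Table 3.

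**Formula** (two means, equal arms, normal approximation)

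Detectable difference = (z0.975 + z0.90) × SD × √(2/500) = (1.9600 + 1.2816) × 0.06325 × SD = 0.2050 × SD

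**Step 1. Reproduce the table**

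| Row | SD | 0.2050 × SD | Stated | Stated / computed |
|---|---|---|---|---|
| PaO2/FiO2 | 73 | 14.97 | 15 | 1.00 |
| ICU-free days | 12.6 | 2.58 | 2.6 | 1.01 |
| IL-6 | 862 | 176.7 | 177 | 1.00 |
| IL-8 | 93 | 19.07 | 19 | 1.00 |
| Shock-free days | 4.93 | **1.01** | **2.23** | **2.21** |

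The method behind the table is confirmed by the other four rows. Only the shock-free-days row departs from it.

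**Step 2. Invert the row**
- SD needed for 2.23 days: 2.23 / 0.2050 = 10.88 days.
- Patients per arm for 90% power at 2.23 days with SD 4.93: 2 × (4.93 × 3.2415 / 2.23)² = 103, against about 500 planned.
- Power for 2.23 days with SD 4.93 and 500 per arm: standard error 4.93 × 0.06325 = 0.312; 2.23/0.312 − 1.96 = 5.19; power above 99.9%.
- Power for 1.01 days if the SD is really 10.88: standard error 10.88 × 0.06325 = 0.688; Φ(1.01/0.688 − 1.96) = about 31%.

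**Step 3. Look for another rule that gives 2.23 from SD 4.93**

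| Variant | Detectable difference (days) |
|---|---|
| Noncentral t, 500 per arm | 1.01 |
| 80% power | 0.87 |
| One-sided 0.05 | 0.91 |
| Final-look nominal level 0.0429 (Table 2) | 1.03 |
| Wilcoxon, worst-case efficiency 0.864 | 1.09 |
| 250 per arm, 90% power | 1.43 |
| 250 per arm, 80% power | 1.24 |

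None comes near 2.23.

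**Step 4. A possible origin, unproven.** At 80% power the ICU-free-days SD of 12.6 gives (1.9600 + 0.8416) × 0.06325 × 12.6 = 2.23. This may be a carry-over from another calculation or a coincidence. If it is the origin, the printed difference never belonged to this row, and the printed SD is still unverified.

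**The case against.** The best defence is that the mismatch has little consequence. Table 3 only illustrates sensitivity. The sample size of 1000 and the stopping boundaries rest on ventilator-free days with an SD of 10.5. Shock-free days is at most one component of a listed secondary endpoint. What a null result excludes will come from the observed confidence interval, not from a planning table. If 4.93 is the correct SD, the trial is more sensitive than stated, which harms nobody. All of this stands and keeps the point minor, but none of it reconciles the two entries.

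A reader might go further and conclude that the SD must be the wrong entry. The argument would be that if deaths scored zero at the table's 22% mortality, a mean of 19.1 days would force an SD of at least √(0.78 × 24.49² − 19.1²) = 10.1, where 24.49 = 19.1/0.78. The protocol does not support this. Zero on death is the rule for ventilator-free days. Section 3.2 credits organ-failure-free days one at a time while the patient is alive and free of the failure, so a patient who dies keeps the days already accrued. The bound therefore cannot be used to choose between the entries.

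A reader might also infer that the wrong figure passes into the analysis plan. That document is not at hand, so this cannot be said.

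**Conclusion.** The point holds as an internal inconsistency in one table row. Under the table's own conditions, SD 4.93 and a detectable difference of 2.23 days disagree by a factor of 2.21. At least one entry is wrong, possibly both, and the protocol does not show which.

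The conclusion assumes equal arms of about 500 and a comparison of means. The protocol states the first. The second follows from the planned analysis and from the agreement of the other four continuous rows. The damage is confined to the stated sensitivity on shock-free days. The sample size, the primary analysis and the stopping rules are unaffected. This is a minor correction.

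**What to change.** Check the shock-free-days SD against the data it came from, then restate the detectable difference as 0.205 × SD:
- if 4.93 is confirmed, replace 2.23 by 1.0 days;
- if the SD proves to be about 10.9, correct the SD and keep 2.23;
- if it is some other value, correct both entries.

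The cost is one look at the source data and one or two table cells. No analysis, sample size or procedure changes.

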8.1 Data Collection

The research coordinators will collect data and record it either on paper data sheets or in a custom-designed computer database. Data will be transferred to the Clinical Coordinating Center on a prescribed basis through a web-based data collection program.

8.2 Site Monitoring

Site visits will be performed on a regular basis by the Data Coordinating Center, to ensure that all regulatory requirements are being met and to monitor the quality of the data collected. Records of Institutional Review Board approvals and patients' charts will be examined on a spot check basis to evaluate the accuracy of the data entered into the database.

9 Risk Assessment

This study involves randomization to one of two interventions: 1) Initial trophic enteral feeds followed by advancement to full-calorie enteral feeds or 2) initial full-calorie enteral feeds. Each carries with it potential risks and potential offsetting benefits..

9.1 Risks of Enteral Feedings

Potential risks of enteral feedings exist in both feeding groups. Common risks of enteral feeding are abdominal distention, cramping, nausea, and diarrhea. Uncommon risks of enteral feeding include vomiting, aspiration, and intestinal ischemia.

9.2 Risks of Full-calorie Enteral Feedings

Potential common risks to patients in the early full-calorie feeding group are more episodes of gastrointestinal intolerance of the tube feedings. GI intolerance includes abdominal distention, abdominal cramping, nausea, vomiting and diarrhea. GI intolerance could lead to more vomiting and aspiration. The early full-calorie feeding group may also experience more diarrhea. Additionally, patients receiving early full-calorie enteral feeds may be at an increased risk for intestinal ischemia or infarction. Because they will receive more calories, patients in this group may be at risk of having higher blood glucoses. The treatment of the higher blood glucoses will be standardized to help control for this confounder, which will likely precipitate the full-calorie feeding group receiving more insulin. The clinical significance of additional insulin is uncertain. Early full-calorie feedings could theoretically reduce the risk of infection by improving nutritional status, but could also be associated with increased infection risk from hyperglycemia or aspiration pneumonia.

9.3 Risks of Trophic Enteral Feedings

Patients in the initial trophic feeding group will receive less calories and protein for the first six days. The clinical importance of this is uncertain, but could lead to more protein catabolism and weight loss. In addition, trophic feedings could reduce immune function and impair control of infections. The trophic feeding group may have a decreased incidence of abdominal distention, abdominal cramping, vomiting, aspiration, and diarrhea.

9.4 Risks of Blood Draws

All patients will have blood drawn for research purposes. The risks of drawing blood are uncommon and include bleeding and bruising. Commonly, drawing blood is painful, and rarely, drawing blood can lead to infections at the site of the blood draw.

9.5 Risk of Death

It is possible that one treatment arm may lead to more deaths and mortality is a secondary outcome and will be monitored during the course of the study.

9.6 Minimization of Risks

Federal regulations at 45 CFR 46.111(a)(1) requires that risks to subjects are minimized by using procedures which are consistent with sound research design. There are several elements of study design inherent in the present protocol that meet this human subject protection requirement. First, several of the exclusion criteria prohibit participation of patients who might be at increased risk of enteral nutrition (e.g. bowel obstruction, bowel ischemia, bowel infarction, severe malnutrition). Safeguards with regard to intolerance of tube feeds have been incorporated into

the protocol, most notably frequent evaluation of residuals and gastrointestinal intolerances (nausea, vomiting, diarrhea, abdominal distention, constipation). Actions to be taken for either elevated residual volumes or gastrointestinal intolerances have been systematically included in the protocol. These actions include adjustments to or temporary discontinuation of the enteral feedings in cases of elevated residual volumes, nausea, diarrhea, and abdominal distention. For diarrhea and constipation, the choice of action is left to the discretion of the treating physician. The DSMB will be reviewing data as outlined above and will examine not only efficacy but safety (inclusive of mortality) and reserves the right to halt the study at any time.

9.7 Potential Benefits

Study subjects may or may not receive any direct benefits from their participation in this study. Full calorie feeds may be result in improved nutritional status and facilitate disease resolution. Trophic feeds may lead to reduction in the volume of recurrent aspiration and avoid prolongation of ALI/ARDS.

9.8 Risks in Relation to Anticipated Benefits

Federal regulations at 45 CFR 46. 111 (a)(2) require that "the risks to subjects are reasonable in relation to anticipated benefits, if any, to subjects, and the importance of the knowledge that may reasonably be expected to result." Based on the preceding assessment of risks and potential benefits, the risks to subjects are reasonable in relation to anticipated benefits.

Procedures – blood draws. The risks associated with these common clinical practices are small, however the knowledge gained in furthering our understanding of the pathophysiology and potentially leading to better and targeted therapy may be substantial.

Treatments – The nutrition regimens chosen are consistent with clinical practice. There is potential for benefit to society and individual patients should one treatment arm prove to be of benefit. Should one treatment arm, again consistent with clinical practices, prove to be harmful, the benefit will be in avoiding such therapies for future patients with ALI/ARDS.

In summary, investigators have reviewed enteral nutrition literature through February 2009 in regard to clinical practices, expert opinions and consensus recommendations and conclude the following:

- 1. Equipoise is present with regard to the nutritional issues to be addressed in this trial (inclusive of but not limited to caloric intake, time to implement full feeding).
- 2. Treatment arms in the EDEN protocol are within the spectrum of clinical practice and the potential risks and benefits have been weighed and equipoise between the nutrition strategies remains.
- 3. Evidence does not support supplementing enteric nutrition with parenteral nutrition, and may actually suggest harm in so doing.

10 Human Subjects

Each study participant or a legally authorized representative must sign and date an informed consent form. Institutional review board approval will be required before any subject is entered into the study.

10.1 Selection of Subjects

10.1.1 Equitable Selection of Subjects

Federal regulations at 45 CFR 46(a)(3) require the equitable selection of subjects. The ICUs will be screened to determine if any patient meets the inclusion and exclusion criteria. Data that have been collected as part of the routine management of the subject will be reviewed to determine eligibility. No protocol-specific tests nor procedures will be performed as part of the screening process. If any subjects meet criteria for study enrollment, then the attending physician will be asked for permission to approach the patient or his/her surrogate for informed consent. Justifications of exclusion criteria are given in Section 4.3. These exclusion criteria neither unjustly exclude classes of individuals from participation in the research nor unjustly include classes of individuals from participation in the research. Hence, the recruitment of subjects conforms to the principle of distributive justice.

10.1.2 Justification of Including Vulnerable Subjects

The present research aims to investigate the safety and efficacy of a type of treatment for patients with acute lung injury and acute respiratory distress syndrome. Due to the nature of these illnesses, the vast majority of these patients will have impaired decision-making capabilities. This study cannot be conducted if limited to enroll only those subjects with retained decision-making capacity. Hence, subjects recruited for this trial are not being unfairly burdened with involvement in this research simply because they are easily available.

10.2 Informed Consent

Federal regulations 45 CFR 46.111(a)(5) require that informed consent will be sought from each prospective subject or the subject's legally authorized representative. The investigator is responsible for ensuring that the patient understands the risks and benefits of participating in the study, and answering any questions the patient may have throughout the study and sharing any new information in a timely manner that may be relevant to the patient's willingness to continue his or her participation in the trial. The consenter will make every effort to minimize coercion. All study participants or their surrogates will be informed of the objectives of the study and the potential risks. The informed consent document will be used to explain the risks and benefits of study participation to the patient in simple terms before the patient is entered into the study, and to document that the patient is satisfied with his or her understanding of the risks and benefits of participating in the study and desires to participate in the study. The investigator is responsible for ensuring that informed consent is given by each patient or legal representative. This includes obtaining the appropriate signatures and dates on the informed consent document prior to the performance of any protocol procedures and prior to the administration of study agent.

10.3 Continuing Consent

For subjects for whom consent was initially obtained from a surrogate, but who subsequently regains decision-making capacity while in hospital, all sites will obtain formal consent for continuing participation, inclusive of continuance of data acquisition. The initial consent form signed by the surrogate should reflect that such consent will be obtained.

10.4 Identification of Surrogates

Many of the patients approached for participation in this research protocol will invariably have limitations of decision-making abilities due to their critical illness. Hence, most patients will not be able to provide informed consent. Accordingly, informed consent will be sought from the potential subject's legally authorized representative.

Regarding proxy consent, the existing federal research regulations ('the Common Rule') states at 45 CFR 46.116 that "no investigator may involve a human being as a subject in research...unless the investigator has obtained the legally effective informed consent of the subject or the subject's legally authorized representative"; and defines at 45 CFR 46 102 (c) a legally authorized representative (LAR) as "an individual or judicial or other body authorized under applicable law to consent on behalf of a prospective subject to the subject's participation in the procedures(s) involved in the research." OHRP defined examples of "applicable law" as being state statutes, regulations, case law, or formal opinion of a State Attorney General that addresses the issue of surrogate consent to medical procedures. Such "applicable law" could then be considered as empowering the surrogate to provide consent for subject participation in the research. Interpretation of "applicable law" is therefore state specific and hence, will be left to the discretion of the individual IRBs of the respective clinical centers involved in the ARDSNet.

According to a previous President's Bioethics Committee (National Bioethics Advisory Committee), an investigator should accept as an LAR...a relative or friend of the potential subject who is recognized as an LAR for purposes of clinical decision making under the law of the state where the research takes place (National Bioethics Advisory Commitee (NBAC), 1998). Finally, OHRP has opined in their determination letters that a surrogate could serve as a LAR for research decision making if such an individual is authorized under applicable state law to provide consent for the "procedures" involved in the research study (Office of Human Research Protections (OHRP), 2002).

10.5 Justification of Surrogate Consent

According to the Belmont Report, respect for persons incorporates at least two ethical convictions; first, that individuals should be treated as autonomous agents, and second, that person with diminished autonomy are entitled to protection. One method that serves to protect subjects is restrictions on the participation of subjects in research that presents greater than minimal risks. Commentators and Research Ethics Commission have held the view that it is permissible to include incapable subjects in greater than minimal risk research as long as there is the potential for beneficial effects and that the research presents a balance of risks and expected direct benefits similar to that available in the clinical setting (Dresser, 1999). Several U.S. task forces have deemed it is permissible to include incapable subjects in research. For example, the American College of Physicians' document allows surrogates to consent to research involving incapable subjects only "if the net additional risks of participation are not substantially greater than the risks of standard treatment." (American College of Physicians, 1989). Finally, the National Bioethics Advisory Committee (NBAC) stated that an IRB may approve a protocol that presents greater than minimal risk but offers the prospect of direct medical benefits to the subject, provided that...the potential subject's LAR gives permission..." (National Bioethics Advisory Committee (NBAC), 1998)

Consistent with the above ethical sensibilities regarding the participation of decisionally incapable subjects in research and the previous assessment of risks and benefits in the previous section, the present trial presents a balance of risks and potential direct benefits that is *similar* to that available in the clinical setting, with the exception of the additional blood draws.

